5.7 APPROPRIATENESS OF MEASUREMENTS

The primary efficacy endpoint (CDAI decrease of \geq 70 compared to baseline) is a standard outcome criterion that is widely accepted for regulatory purposes to demonstrate efficacy on signs and symptoms of CD.

Therefore, the appropriateness of all measurements applied in this trial is assured and is in line with guidance from regulatory authorities (R13-2623).

Page 56 of 93

Proprietary confidential information © 2017 Boehringer Ingelheim International GmbH or one or more of its affiliated companies

6. INVESTIGATIONAL PLAN

6.1 **VISIT SCHEDULE**

A schedule of assessments is provided in Flow Chart A and Flow Chart B.

Visits will be scheduled as close as possible to the preplanned schedule:

- A visit window of -1/+2 days is permitted for Visit 2 (Day 1)
- A visit window of ± 1 day is permitted for Visit 3 to Visit 4
- A visit window of ± 3 days is permitted for Visit 5 to Visit 25, and EoT
- A visit window of +7 days is permitted for safety follow-up Visit
- Trial medication will be administered every 2 weeks (±1 day up to Visit 4 and ±3 days from Visit 5 onwards).

On trial medication administration days, all assessments should be performed prior to administration, unless otherwise specified. Laboratory samples must be drawn prior to trial medication injection.

6.2 DETAILS OF TRIAL PROCEDURES AT SELECTED VISITS

Study procedures to be performed at each visit are listed in Flow Chart A, Flow Chart B, and the respective protocol sections. Refer to Section 5 for explanations of procedures.

6.2.1 Screening and run-in period(s)

The Screening period in this trial will comprise two separate visits. Once the patient has provided informed consent (before any trial-specific procedures or assessments are performed), meets the inclusion criteria and does not meet any of the exclusion criteria (see Section 3.3), the trial site will enter the screened patient into the system using the IRT.

Screening Visit 1, Day -28 to Day -14

The following will be performed/collected:

- Demographic information (including gender, date of birth, ethnicity, and race), and medical and surgical history (including CD history and history of opportunistic infection)
- Infection screen (HBsAg, antiHCV, and HIV test, per the investigator's discretion and/or where mandated by local authorities)
- Chest X-ray, unless taken within the previous 12 weeks (see Section 5.3.5.1)
- TB test (IGRA e.g., QuantiFERON[®] Gold assay; see Section 5.3.5.1)
- Stool studies to evaluate for enteric pathogens (see Section 5.3.3)
- Serum pregnancy test for women of childbearing potential
- Physical examination, including height (cm) and weight (kg) (see Section 5.3.1)
- Vital signs (blood pressure, pulse rate, and body temperature; see Section 5.3.2)
- Laboratory testing (serum chemistry, hematology, and urinalysis; see Section 5.3.3)

Page 57 of 93

Proprietary confidential information © 2017 Boehringer Ingelheim International GmbH or one or more of its affiliated companies

- 12-lead ECG (see Section 5.3.4)
- Previous and concomitant therapy (see Section 4.2)
- Assessment of AEs (see Section 5.3.6)

Following completion of the above screening procedures at Visit 1, patients who are eligible to continue will receive a patient CDAI diary to complete their daily symptoms during the 7-day period immediately before Visit 1.1. Sites must ensure that sufficient time is allowed between Visit 1 and Visit 1.1 to allow completion of the CDAI diary.

Screening Visit 1.1, Day -9

At Visit 1.1, the patient CDAI diary will be reviewed by the investigator in order to assess the CDAI score. The hematocrit result and weight measurement from Visit 1 must be used to calculate the CDAI score at Visit 1.1 (see Section 5.2.1). Only patients with moderate to severe CD, defined as CDAI score \geq 220 and \leq 450 will undergo an endoscopy at Visit 1.1 (see Section 5.2.2). Evidence of mucosal ulcers in at least one segment of the ileum or colon and a SES-CD score \geq 7 (or \geq 4 for patients with isolated ileal disease) must be confirmed by central independent reviewer(s) prior to randomization.

Once patients have completed screening at Visit 1.1, have met all the inclusion criteria and have not met any of the exclusion criteria, randomization will occur on Day 1 (-1/+2) through a standard randomization visit call, using the IRT system. Patients will be randomized to each treatment in a 1:1 ratio (BI 695501: EU-approved Humira) according to the stratification factors. Patients will be randomly assigned in a blinded fashion to BI 695501 or EU-approved Humira as described in Section 4.1.3 and Section 7.6.

6.2.2 Treatment period(s)

Prior to Week 24, BI 695501/EU-approved Humira will be administered by a suitably qualified, designated unblinded trial personnel. From Week 24 onwards, when all patients will be receiving BI 695501, it will not be necessary for the trial personnel administering the medication to be unblinded. However, patients and other trial personnel must remain blinded with respect to the initial assignment to EU-approved Humira or BI 695501. All administrations of trial medication will be performed at the trial site. Trial medication will be administered every 2 weeks (-1/+2 days at Visit 2, ± 1 day up to Visit 4 and ± 3 days from Visit 5 onwards).

Baseline, Visit 2 (Day 1)

Eligible patients will be randomized and will receive their first administration of trial medication on Day 1.

The following will also be performed/collected:

- Physical examination, including weight (kg) (see Section 5.3.1)
- Vital signs (blood pressure, pulse rate, and body temperature; see Section 5.3.2)

- Laboratory testing (serum chemistry, hematology, and urinalysis; see Section 5.3.3)
- Urine pregnancy test (in addition to a serum pregnancy test at Screening)
- Evaluation of CDAI (see Section 5.2.1)
- Previous and concomitant therapy (see Section 4.2)
- Assessment of AEs (see Section 5.3.6)
- Contact IRT and administer first trial medication injection (see Section 4.1.4)

Visit 3 (Day 15)

The following will be performed/collected:

- Vital signs (blood pressure, pulse rate, and body temperature; see Section 5.3.2)
- Previous and concomitant therapy (see Section 4.2)
- Assessment of AEs (see Section 5.3.6)
- Contact IRT and administer trial medication

Visits 4 and 14 (Days 29 and 169, respectively)

The following will be performed/collected:

- Physical examination, including weight (kg) (Visit 14 only; see Section 5.3.1)
- Vital signs (blood pressure, pulse rate, and body temperature; see Section 5.3.2)
- Laboratory testing (serum chemistry, hematology, and urinalysis; see Section 5.3.3)
- Urine pregnancy test for women of childbearing potential (Visit 14 only)
- Local hematocrit testing (Visit 4 only; to be used for CDAI evaluation)
- Evaluation of CDAI (see Section 5.2.1)
- TB test (IGRA e.g., QuantiFERON Gold assay; at Visit 14 only)
- 12-lead ECG (see Section 5.3.4)
- Previous and concomitant therapy (see Section 4.2)
- Assessment of AEs (see Section 5.3.6)
- Contact IRT and administer trial medication

At Visit 14, patients initially randomized to EU-approved Humira will switch to receive BI 695501. From Visit 14 onwards, all patients will be receiving BI 695501.

Page 59 of 93

Proprietary confidential information © 2017 Boehringer Ingelheim International GmbH or one or more of its affiliated companies

Visits 6, 10, 18 and 22 (Days 57, 113, 225 and 281, respectively)

The following will be performed/collected:

- Vital signs (blood pressure, pulse rate, and body temperature; see Section 5.3.2)
- Laboratory testing (serum chemistry, hematology, and urinalysis; see Section 5.3.3)
- Urine pregnancy test for women of childbearing potential
- 12-lead ECG (Visit 6 only; see Section 5.3.4)
- Previous and concomitant therapy (see Section 4.2)
- Assessment of AEs (see Section 5.3.6)
- Contact IRT and administer trial medication

Visit 8 (Day 85)

The following will be performed/collected:

- Vital signs (blood pressure, pulse rate, and body temperature; see Section 5.3.2)
- Previous and concomitant therapy (see Section 4.2)
- Assessment of AEs (see Section 5.3.6)
- Evaluation of CDAI (see Section 5.2.1)
- Contact IRT and administer trial medication

At this visit, the hematocrit value from the central laboratory assessment at Visit 6 (Day 57) will be used to determine CDAI score.

Visits 12 and 16 (Days 141 and 197, respectively)

The following will be performed/collected:

- Vital signs (blood pressure, pulse rate, and body temperature; see Section 5.3.2)
- Previous and concomitant therapy (see Section 4.2)
- Assessment of AEs (see Section 5.3.6)
- Contact IRT and administer trial medication

Trial medication administration only visits

Visits 5, 7, 9, 11, 13, 15, 17, 19, 20, 21, 23, 24, and 25 are for administration of trial medication only and the following will be performed:

• Contact IRT and administer trial medication

Page 60 of 93

Proprietary confidential information © 2017 Boehringer Ingelheim International GmbH or one or more of its affiliated companies

End of Treatment Visit

The following will be performed/collected:

- TB test (IGRA e.g., QuantiFERON[®] Gold assay)
- Physical examination, including weight (kg) (see Section 5.3.1)
- Vital signs (blood pressure, pulse rate, and body temperature; see Section 5.3.2)
- Laboratory testing (serum chemistry, hematology, and urinalysis; see Section 5.3.3)
- Urine pregnancy test for women of childbearing potential
- 12-lead ECG (see Section 5.3.4)
- Evaluation of CDAI (see Section 5.2.1)
- CRP (see Section 5.2.3)
- Previous and concomitant therapy (see Section 4.2)
- Assessment of AEs (see Section 5.3.6)

Patients who discontinue the trial at any time after Day 1 (but do not withdraw their consent) will be required to have all of the evaluations for the EoT Visit as soon after trial discontinuation as possible (except TB test, which is not required for those discontinuing before the maintenance phase, which is only required for patients who complete the 48-week treatment period).

The patient who early discontinued from the trial will receive treatment as deemed appropriate by the investigator and in accordance with the applicable guidance.

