3. DESCRIPTION OF DESIGN AND TRIAL POPULATION

3.1 OVERALL TRIAL DESIGN AND PLAN

This is an exploratory, randomized, 56-week, double-blind, parallel arm, multiple dose, active comparator trial of BI 695501 and EU-approved Humira, with a 48-week treatment period and a 10-week follow-up period (starting after last dose of trial medication at Week 46) in patients with moderately to severely active CD, and a primary endpoint assessment at Week 4.

The trial will consist of a Screening period of up to a maximum of 28 days, a 48-week treatment period consisting of an induction period from Baseline to Week 4 and a maintenance period from Week 5 to Week 48, and a 10-week safety follow-up period (starting after last dose of trial medication at Week 46).

Approximately 130 evaluable patients with moderately to severely active CD will be randomized into the trial. Patients will be randomly assigned to receive either BI 695501 or EU-approved Humira according to the randomization ratio and the stratification factors as described in Section 7.6. Each patient will receive a loading dose of 160 mg of BI 695501 or EU-approved Humira (Day 1), followed by 80 mg of BI 695501 or EU-approved Humira 2 weeks later (Day 15), and thereafter 40 mg of BI 695501 or EU-approved Humira every 2 weeks until the end of the treatment period (Week 46; with End of Treatment [EoT] evaluations at Week 48). Trial medication will be administered by s.c. injection.

At Week 4, patients will be assessed and those who are classified as responders (CDAI decrease of \geq 70 compared to baseline) will continue on trial and enter the maintenance phase. Patients who are originally randomized to EU-approved Humira will switch to BI 695501 at Week 24.

Patients will undergo up to 27 visits (including 13 trial medication administration only visits) over the duration of the trial (56 weeks). The trial procedures to be undertaken at each visit are shown in Flow Chart A and Flow Chart B.

The primary endpoint of the trial is the proportion of patients in each treatment group with a clinical response (CDAI decrease of \geq 70 compared to baseline) at Week 4. The primary analysis will take place when the last patient has completed the Week 4 assessments. For more details, please refer to Section 7.4.1.

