4.1.1 Identity of the Investigational Medicinal Products

BI 695501 and EU-approved Humira will be used in this trial. Details of the trial medication are provided in Table 4.1.1: 1 and Table 4.1.1: 2.

Table 4.1.1: 1	Test product
----------------	--------------

Substance:	BI 695501	
Pharmaceutical formulation:	Solution for injection in PFS	
Source:	BI Pharma GmbH & Co. KG, Germany	
Unit strength:	40 mg / 0.8 mL	
Posology	 160 mg on Day 1 (after randomization); 80 mg on Day 15 (Week 2); 40 mg every 2 weeks from Week 4 to Week 46 inclusive (and from Week 24 to Week 46 inclusive for patients switching from EU-approved Humira) 	
Route of administration:	subcutaneous injection	

Table 4.1.1: 2Reference product

Substance:	EU-approved Humira (adalimumab)	
Pharmaceutical formulation:	Solution for injection in PFS	
Source:		
Unit strength:	40 mg / 0.8 mL or 40 mg / 0.4 mL	
Posology	160 mg on Day 1 (after randomization);80 mg on Day 15 (Week 2);40 mg every 2 weeks from Week 4 to Week 22 inclusive	
Route of administration:	subcutaneous injection	

BI 695501 will be provided in sterile, preservative-free, non-pyrogenic, single-use PFS containing 40 mg of BI 695501 per 0.8 mL. On Day 1, four PFS will be used (total of 160 mg); on Day 15 (Week 2), two PFS will be used (total of 80 mg); and thereafter (Week 4, then every 2 weeks until Week 46 if patient is eligible to enter the maintenance phase; also

Boehringer Ingelheim		12 Dec 2017
BI Trial No.: 1297.4		
c09542349-05	Trial Protocol	Page 33 of 93

from Week 24 to Week 46 for patients who switch from EU-approved Humira), one PFS will be used per injection.

EU-approved Humira will be provided in sterile, preservative-free, non-pyrogenic, single-use PFS containing 40 mg of adalimumab per 0.8 mL or 40 mg of adalimumab per 0.4 mL (old and new formulations, respectively, approved to be comparable). On Day 1, four PFS will be used (total of 160 mg); on Day 15 (Week 2), two PFS will be used (total of 80 mg); and thereafter (Week 4, then every 2 weeks until Week 22 if patient is eligible to enter the maintenance phase), one PFS will be used per injection.

Any unused product or waste material will be disposed of in accordance with local requirements.

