5.1.2 Secondary Endpoint(s)

Secondary endpoints are:

Efficacy

- Proportion of patients in each treatment group with a clinical response (CDAI decrease of ≥70 compared with baseline) at Week 24
- Proportion of patients in each treatment group in clinical remission (CDAI <150) at Week 24

Safety

- Proportion of patients with AEs, SAEs, and AESIs (e.g., serious infections, allergic reactions, abscesses, fistula, strictures)
- Proportion of patients with infections/serious infections (seriousness of infection defined as requirement of i.v. antibiotics for treatment and/or meeting seriousness criteria to be qualified as an SAE)
- Proportion of patients who experience hypersensitivity reactions
- Proportion of patients who experience DILI
- Proportion of patients with injection-site reactions

Page 41 of 93

Proprietary confidential information © 2017 Boehringer Ingelheim International GmbH or one or more of its affiliated companies

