Proprietary confidential information © 2017 Boehringer Ingelheim International GmbH or one or more of its affiliated companies

Site staff blinding procedure

Responsibilities for blinded and unblinded study site staff are defined below. At each site, a form with the name(s) of the staff members, blinded and unblinded, with their respective responsibilities will be filled in.

(NOTE: all personnel noted below will have signed the Site Personnel Signature Log, clearly outlining each individual's responsibility).

In case of non-availability of blinded or unblinded study staff, the CRO and sponsor should be informed immediately.

Blinded Personnel	Main Responsibilities			
Principal Investigator: CANNOT ADMINISTER THE MEDICATION	 Remains blinded to the medication assignment during the whole trial Monitors patient status Responsible for the delegation of tasks to appropriate staff and to ensure correctness of all assessments Provides direct patient care Works and communicates with blinded CRA Ensures adequate unblinded trial site personnel and facilities for administration of trial medication Contacts IXRS[®] to enter screen failures, screened patients, randomizations, and obtain subsequent medication assignments 			
Blinded Sub-Investigator or Study Coordinator/Study Nurse: CANNOT ADMINISTER THE MEDICATION	 Remains blinded to the medication assignment during the whole trial Contacts IXRS[®] to enter screen failures, screened patients, randomizations, and obtain subsequent medication assignments Monitors patient status Provides direct patient care, if applicable Works and communicates with blinded CRA Can be involved in the receipt, storage control and return of IP (since secondary package is blinded) 			
Blinded CRA: CANNOT MAKE SAFETY OR EFFICACY EVALUATIONS CANNOT ADMINISTER THE MEDICATION	 Remains blinded to the medication assignment during the whole trial Acts as the primary point of contact for the blinded and unblinded site team Provides ongoing site support in all areas of trial conduct and performs accountability and reconciliation of trial medication (after disposal of the syringes by the unblinded trial medication administrator) Conducts blinded site monitoring visits and performs source document verification 			

CRA = clinical research associate

Page 79 of 93

Proprietary confidential information © 2017 Boehringer Ingelheim International GmbH or one or more of its affiliated companies

Unblinded Personnel	Main Responsibilities

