Unblinded Trial Medication Administrator (Sub-Investigator or Study Nurse): CANNOT MAKE SAFETY OR EFFICACY EVALUATIONS	 Prepares trial medication for dispensing Performs the trial medication administration and ensures patient is blinded during IP administration Discard used syringes in a blinded fashion after administration of trial medication according to local procedures such as local SOPs Retains used unsealed/opened boxes (secondary packaging), which contained the syringes before administration of trial medication, for reconciliation by blinded CRA prior to destruction Works and communicates with the blinded CRA in a way that does not reveal the treatment arm Can be involved in the receipt, storage control, and return of trial medication

Training

All professional personnel taking part in the clinical trial are trained and aware of the need to respect study blinding principles as foreseen by the protocol. Blinded and unblinded trial site staff, as well as blinded CRAs, will be trained on trial blinding procedures before the start of any trial activities at site. Unblinded trial site staff is restricted to persons handling trial medications including the injection of trial drug. Training in study blinding procedures for blinded trial CRAs will be provided during a CRA Meeting. Training in trial blinding procedures for blinded and unblinded site staff will be provided at the Investigators' Meeting. For the remaining site staff, who do not participate in an Investigators' Meeting, applicable training in trial blinding procedures will be provided by a blinded CRA during the Site Initiation Visit, based on information in the CTP, Medication Blinding Procedures, and Pharmacy Manual. Such training is a part of trial specific agenda for Site Initiation Visit, as well as the slide presentation prepared for the visit. All training will be documented.

09542349-05Trial ProtocolPage 80 of 93Proprietary confidential information © 2017 Boehringer Ingelheim International GmbH or one or more of its affiliated companies

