16.1.7.5. Injection-site reactions

Injection-site reactions are those events recorded with MedDRA high level terms (as listed in BICMQs

Administration site reaction subsearches 1,2,4 and 5, with a version consistent with the MedDRA version, refer to APPENDIX 4):

- Administration site reactions NEC
- Application and instillation site reactions
- Infusion site reactions
- Injection site reactions

These will be presented by period and treatment.

There are 2 periods:

Document: \\ieedc-
vnasc01\BIOSdata\Boehringer_Ingelheim\BI_695501\NVA96252\Biostatistics\Documentation\S
AP\BI1297.4 SAP FINAL v4.0_22MAY2019.docx

Author: Version Number: Final V4.0
Version Date: 22MAY2019

Template No: CS_TP_BS016 Revision 5
Effective Date: 01Apr2018

Reference: CS_WI_BS005

Period 1	Visit date within [first injection date; Week 24 Visit[+10 weeks (70 days) inclusive (for patients that discontinued the treatment before week 24).
Period 2	Visit date within 
 • [Week 24 Visit; Week 56 Visit[or • [Week 24 visit; last injection date + 10 weeks (70 days)] (for patients that discontinued the treatment before week 56)].

Injection-site reactions will be listed.

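### No adverse-event question is scheduled at 13 of the 24 injection visits, and the wait for the next one reaches 6 to 8 weeks for some injections from Week 32, all of them BI 695501

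*Protocol*

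**What the plan says.** Protocol 6.2.2 states that "Visits 5, 7, 9, 11, 13, 15, 17, 19, 20, 21, 23, 24, and 25 are for administration of trial medication only". The only task listed for these visits is to contact the IRT and give the injection. Section 3.1 gives the same count: "Patients will undergo up to 27 visits (including 13 trial medication administration only visits". Flow Chart B agrees: its AE and concomitant-therapy rows are marked only at Weeks 4, 8, 12, 16, 20, 24, 28, 32, 40 and 48 and at the Week 56 follow-up.

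The footnotes on dosing in both flow charts, and section 6.1, put assessments before the injection at each visit unless stated otherwise. Section 4.1.4 requires at least one hour of on-site observation after the injections at Visits 2 and 14 only.

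Protocol 5.1.2 names as a secondary endpoint: "Proportion of patients with injection-site reactions". SAP 16.1.7.5 says of these reactions: "These will be presented by period and treatment". The periods divide at the Week 24 visit. For the overall AE analysis, Protocol 7.3.4 assigns events after the first BI 695501 dose to BI 695501, including in patients who switch from EU-approved Humira.

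**The concern.** An injection-site reaction is usually mild and short-lived, and is easily forgotten if nobody asks about it soon afterwards. The patient attends every two weeks, yet at more than half of the injection visits no question is planned. The intervals between questions also lengthen late in the trial, when every patient is receiving BI 695501.

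Safety after the switch is one of the trial's stated purposes (Protocol 2.1 and 3.2). Sparser questioning in that part of the trial could lower the recorded frequency of minor events in Period 2. It could do the same for BI 695501 in the overall AE analysis, for which risk ratios and risk differences with 95% confidence intervals are planned.

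**Working it through.** **Inputs**
- Injections: Day 1, Week 2, then "40 mg every 2 weeks from Week 4 to Week 46 inclusive" (Protocol 4.1.1). This gives Weeks 0, 2, ..., 46, or 46/2 + 1 = 24 injection visits, Visits 2 to 25. Visit v falls at Week 2(v − 2).
- EU-approved Humira is given to Week 22 only (4.1.1); from Week 24 all patients receive BI 695501.
- Visits with an AE assessment: Weeks 0, 2 and 4 (Flow Chart A); "Visits 6, 10, 18 and 22 (Days 57, 113, 225 and 281, respectively") in 6.2.2, which are Weeks 8, 16, 32 and 40; Visit 8 (Week 12); Visits 12 and 16 (Weeks 20 and 28); Visit 14 (Week 24); End of Treatment (Week 48); and follow-up (Week 56).

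**Reproducing the plan's count.** The list in 6.2.2 has 13 visits, matching section 3.1. Then 13/24 = 54% of injection visits have no AE question and 24 − 13 = 11 have one. Five of the 13 come before Week 24 (Visits 5, 7, 9, 11, 13). Eight come after it (Visits 15, 17, 19, 20, 21, 23, 24, 25).

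**Lag** = week of the next later visit with an AE assessment − week of the injection. A same-day assessment does not count, because it precedes the injection.

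| Injection weeks | Lags (weeks) | Mean | Maximum |
|---|---|---|---|
| 0–22 | 2, 2, 4, 2, 4, 2, 4, 2, 4, 2, 4, 2 | 34/12 = 2.83 | 4 |
| 24–30 | 4, 2, 4, 2 | 12/4 = 3.0 | 4 |
| 32–46 | 8, 6, 4, 2, 8, 6, 4, 2 | 40/8 = 5.0 | 8 |
| 24–46 | the two rows above | 52/12 = 4.33 | 8 |

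The four lags above 4 weeks belong to the injections at Weeks 32 and 40 (8 weeks each) and Weeks 34 and 42 (6 weeks each).

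**Consequence for the overall AE analysis.** Take one patient from each arm, both treated to Week 46. Injections counted under BI 695501 are 24 + 12 = 36, with mean lag (34 + 52 + 52)/36 = 3.83 weeks; 4 + 4 = 8 of them have a lag above 4 weeks. Injections counted under EU-approved Humira are 12, with mean lag 2.83 weeks and none above 4 weeks.

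Lags are nominal and ignore the visit windows. They describe the schedule; they are not an estimate of missed events.

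**The case against.** The schedule is internally consistent, and how often to ask about AEs is a judgement in an exploratory trial with no confirmatory hypotheses. The endpoint counts patients with any reaction, so one forgotten episode need not change a patient's status. The SAP plans no test of Period 2 against Period 1, and that contrast is not clean anyway: Period 2 contains only Week 4 responders still on treatment, while Period 1 includes the multi-syringe doses. The overall analysis also gives BI 695501 longer exposure, which works against a shortfall in its counts. All of this stands, and it limits the point to ascertainment of minor events.

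A reader might infer several stronger things that the documents do not support:

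- *That nobody asks about AEs at these visits.* What is missing is a scheduled question. Protocol 5.3.6.2 requires AE collection from consent to 10 weeks after the last dose. Blinded staff have monitoring of the patient among their duties (Appendix 10.1), and unscheduled visits are allowed. None of this guarantees that a minor reaction is elicited, but it rules out the stronger statement.
- *That the blinding rule causes the long lags.* The instruction "CANNOT MAKE SAFETY OR EFFICACY EVALUATIONS" in Appendix 10.1 applies to the unblinded administrator, who injects only until Week 22. It covers 5 of the 13 visits, and no injection before Week 24 has a lag above 4 weeks. From Week 24 any trained member of the trial staff may inject, with no such bar stated.
- *That questioning thins out at the switch.* Weeks 24 to 30 keep the 4-week spacing used from Week 4, and the switch injection has its own hour of observation. The spacing widens only from Week 32.
- *That the randomised comparison is biased.* Both arms follow one schedule, so contrasts between arms within a period are not differentially affected.
- *That the flow charts have no injection-site row.* The published charts are incomplete: footnote 11 is absent from Flow Chart A and footnote 8 from Flow Chart B. The synopsis safety criteria break off in the middle of an injection-related item.
- *That a serious infection could pass unrecorded before the next injection.* Serious infections are AEs of special interest with 24-hour reporting, and patients must consult the investigator before starting new medication. The schedule alone does not show such a failure.

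**Conclusion.** The point holds as one of ascertainment. Thirteen of 24 injection visits (54%) have no scheduled AE or concomitant-therapy question. The nominal lag to the next question is at most 4 weeks for injections before Week 32, and 6 to 8 weeks for four injections after that. Those four are all BI 695501 injections, so any loss of mild, transient events falls on Period 2 and on the BI 695501 side of the overall AE analysis. The documents give no under-reporting rate, so neither the size of a shortfall nor its net effect on any risk ratio can be stated.

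This assumes that visits run at their nominal weeks, that recall of minor reactions fades over several weeks, and that no redacted row schedules an injection-site check at the 13 visits. Their description as administration-only supports the last assumption. The point does not touch the primary endpoint. It is a worthwhile, inexpensive improvement to the secondary safety data.

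**What to change.** Amend Flow Chart B and Protocol 6.2.2 to add an AE question, including the site of the last injection, and concomitant therapy at Visits 5, 7, 9, 11, 13, 15, 17, 19, 20, 21, 23, 24 and 25. Have the answers recorded before the injection by the blinded staff who, under Appendix 10.1, already contact the IRT to "obtain subsequent medication assignments". This leaves the separation between injecting and assessing intact. Every nominal lag then becomes 2 weeks, before and after Week 24.

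The cost is a protocol amendment, one eCRF question set and a few minutes per visit; no visits are added. If these visits have already taken place, SAP 16.1.7.5 and the clinical trial report should state that questioning was sparser from Week 32. They should also caution against reading a lower Period 2 frequency as a product or switch effect.
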